1.3.6.3 Sample size

Participating practices will be randomised to one of three arms. In calculating sample size for cluster randomised trials³¹, it is necessary to take into account within-cluster variance, measured

by an intra-class correlation (ICC). Our experience in previous studies suggests that intra-class correlations of 0.05 for quality of life outcome are typical.

Preliminary analysis of data from the average-sized practices of one of the applicants suggests that there will be approximately 40 patients in such a practice meeting eligibility criteria (1.3.4). We recognise that patients in practices allocated to the diet and lifestyle arms of the trial may be reluctant to undertake a change to their diet or lifestyle and may therefore withhold consent to participate. It is in anticipation of this risk that we have made the assumption that only 30 out of 40 patients identified will agree to participate and that only 25 will provide follow up data for 12 months.

Our primary outcome is a continuous variable – score on a quality of life (QoL) scale. In the absence of detailed data on the distribution of QoL scores in our population, we can nonetheless specify the effect size that we wish to detect. We arbitrarily set this at 0.3 standard deviations on the condition-specific quality of life scale. Within the literature on quality of life assessment, there is a growing consensus³² that an effect size (i.e. change over time divided by standard deviation at baseline) of less than 0.2 represents a negligible change, an effect size of 0.2 up to 0.5 represents a 'small' effect, an effect size of 0.5 up to 0.8 represents a 'moderate' change and an effect size of in excess of 0.8 represents a 'large' change. These criterion values, which have been shown to be stable across a range of settings, have been established by reference to what clinicians and patients consider to be an 'important' difference – the emphasis is therefore on clinical rather than statistical significance. Our proposed effect size of 0.3 therefore represents the difference between the threshold values for 'small', 'moderate' and 'large' changes (0.5 – 0.2; 0.8 – 0.5).

It is important to note that the LIFELAX trial is not a comparison of an intervention with placebo or with normal practice. Instead, there are three active treatment groups. It is not unreasonable to assume that we might observe at least a small change over time in symptom-related and quality of life outcomes in all of these treatment groups. What we are primarily interested in is whether one intervention offers a relative advantage over the others. For example, if the changes over time for the laxative and standardised diet and lifestyle interventions were 'small' by the established criteria set out above, but a 'moderate' improvement was observed in the individualised diet and lifestyle arms, we might reasonably conclude that this intervention offered a relative advantage.

For an effect size of 0.3, 90% power, a significance level of 5%, an intra-class correlation of 0.04, and the ability to recruit and retain 25 patients per practice, we therefore need a total of 57 practices (19 per arm).

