1.3.6 Sampling design and implementation

1.3.6.1 Practice recruitment and randomisation

General practices in England and Scotland will be invited by letter to participate. Standard sample size calculations for a cluster randomised trial³¹ indicate that we will need to recruit 57 practices in total (1.3.6.3). This estimate is based on the number of patients likely to be available in the average-sized practice; if larger practices participate, the number of practices required may be slightly reduced. We will initially seek to include practices from local primary care research networks but may need to supplement with others, depending on take up. Practices agreeing to take part in the study will be randomised by computer to one of the three arms. We recognise that practices may have preferences with respect to allocation of interventions. We will make it very clear to the practices approached to participate in the LIFELAX study that allocation to intervention will be completely at random and that practice preferences cannot be taken into account. Randomisation will be carried out by an individual not otherwise involved in practice contact, or in data analysis.

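### The sample size section calls an ICC of 0.05 typical but calculates with 0.04, unexplained; at 0.05, 57 practices give about 86–88% power, not 90%

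*Protocol*

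**What the plan says.** Section 1.3.6.3 of the protocol sets out the inputs in this order.

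- **ICC evidence:** "Our experience in previous studies suggests that intra-class correlations of 0.05 for quality of life outcome are typical". This is the only evidence on the ICC in the document, and it concerns the same type of outcome as the primary one.
- **Cluster size:** of about 40 eligible patients in an average practice, "only 30 out of 40 patients identified will agree to participate and that only 25 will provide follow up data for 12 months".
- **Target difference:** "We arbitrarily set this at 0.3 standard deviations on the condition-specific quality of life scale".
- **Calculation:** "For an effect size of 0.3, 90% power, a significance level of 5%, an intra-class correlation of 0.04", with 25 patients recruited and retained per practice. The result is 57 practices, 19 per arm.

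Section 1.3.6.1 repeats the total, saying that standard cluster-trial calculations "indicate that we will need to recruit 57 practices in total". Section 1.3.7 plans mixed models with the three arms as fixed effects and baseline data as a covariate. The sample size section does not refer to that adjustment.

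**The concern.** The ICC put forward as evidence is not the ICC used. Nothing in the protocol explains the step from 0.05 to 0.04, so a reader cannot tell whether 0.04 is a slip, a leftover from another calculation or a deliberate choice.

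The choice matters because clustering roughly doubles the required sample here, and the number of practices follows directly from the ICC. The 90% power is the figure against which the trial's size will be judged. If 0.05 applies, that figure is somewhat too high. All three arms receive active treatment and section 1.3.6.3 makes relative advantage the question, so a finding of no difference is a realistic outcome. The stated power should then rest on a consistent premise.

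**Working it through.** **Inputs, all from section 1.3.6.3:** difference 0.3 SD; power 90%; significance level 5%; m = 25 patients per practice, already net of refusal and loss; k = 19 practices per arm; ICC 0.04 (used) or 0.05 (called typical). The text does not say whether the 5% is one- or two-sided; two-sided is taken because it reproduces the stated figure.

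**Formulas** (pairwise comparison of two means, normal approximation):
- Unclustered n per arm = 2(z₀.₉₇₅ + z₀.₉₀)² / 0.3² = 2(1.960 + 1.282)² / 0.09 = 233.5
- Design effect DE = 1 + (m − 1) × ICC
- Practices per arm = 233.5 × DE / 25, rounded up
- Standard error of the difference, in SD units = √(2 × DE / (k × m)), with k × m = 19 × 25 = 475

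**Step 1: reproduce the plan's figure (ICC 0.04).**
- DE = 1 + 24 × 0.04 = 1.96
- 233.5 × 1.96 = 457.7 patients; 457.7 / 25 = 18.3, so 19 per arm and 57 in total. This matches.
- Power: 0.3 / √(2 × 1.96 / 475) = 3.302; 3.302 − 1.960 = 1.342, giving 91.0%. t-based power is 89.5% (36 df, two arms) to 90.0% (54 df, three arms).
- Other readings of the method do not give 19 at ICC 0.04. One-sided 5% gives 15 per arm; dividing the 5% by 2 or by 3 for multiple comparisons gives 22 or 24. At ICC 0.05 the same four options (two-sided, one-sided, divided by 2, divided by 3) give 21, 17, 25 and 27, so none of them reaches 19.

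**Step 2: repeat with ICC 0.05.**
- DE = 1 + 24 × 0.05 = 2.20
- 233.5 × 2.20 = 513.7 patients; 513.7 / 25 = 20.5, so 21 per arm and 63 in total. That is 6 more practices, and 63 × 25 = 1,575 patients followed up against 57 × 25 = 1,425.
- Power with 19 per arm: 0.3 / √(2 × 2.20 / 475) = 3.117; 3.117 − 1.960 = 1.157, giving 87.6%. t-based power is 85.8% (36 df) to 86.5% (54 df).
- Difference detectable with 90% power: (1.960 + 1.282) × √(2 × 2.20 / 475) = 3.242 × 0.0962 = 0.312 SD; t-based, about 0.32 SD.

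**Step 3: the margin.** The largest ICC at which 19 practices of 25 keep 90% power (normal approximation) is (475 / 233.5 − 1) / 24 = 0.043.

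| ICC | Practices per arm for 90% | Total | Power with 57, normal | Power with 57, t-based |
|---|---|---|---|---|
| 0.04 | 19 | 57 | 91.0% | 89.5–90.0% |
| 0.05 | 21 | 63 | 87.6% | 85.8–86.5% |

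**Step 4: possible offsets that the calculation does not claim** (ICC 0.05, normal approximation).
- *Baseline adjustment.* The protocol gives no baseline–outcome correlation r. Scaling the outcome variance by 1 − r² and leaving the ICC unchanged, power is 88.9% for an assumed r of 0.2, 90.4% for 0.3, 92.5% for 0.4 and 94.9% for 0.5.
- *More patients at three months.* The 25 per practice is a 12-month figure, while the primary outcome is at three months. If all 30 consenting patients responded, DE = 1 + 29 × 0.05 = 2.45 and power is 89.9%. Reaching 90% with 19 per arm needs 31 per practice.

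**The case against.** The strongest reply is that nothing has been miscalculated: 57 follows from the stated inputs, and at 0.04 the design has its 90% by the normal approximation. That stands. A reader might infer that the sample size contains an arithmetic error, or that 57 practices cannot deliver the stated power. The document supports neither. It offers 0.05 as a typical value from the team's experience, not as an estimate for this scale and population, and it does not show which of the two values is right.

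The reply also has force on size. The move from 0.30 to 0.312 SD is small beside a target difference that the protocol itself calls arbitrary. Part of the gap between 90% and the t-based 86% comes from the t correction and not the ICC, since 0.04 gives only 89.5–90.0% on that basis. The baseline covariate in section 1.3.7 could restore 90% with an assumed correlation of about 0.3 (normal approximation), and three-month response may exceed 25 per practice. A null result would also be read from the interval estimates that section 1.3.7 promises, not from planned power alone.

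These points limit the consequence. They do not reconcile the two values. The stated calculation is unadjusted, and relying on baseline adjustment or on better three-month response would be a different justification, which the protocol does not make.

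**Conclusion.** The inconsistency is real and the power statement needs correction or justification, but its effect is modest. Section 1.3.6.3 uses an ICC lower than the one it calls typical and does not say why. If 0.05 applies, 57 practices of 25 patients have 87.6% power (normal approximation) or about 86% (t-based) for 0.3 SD, a loss against the stated 90% of about 2.4 or 4 percentage points. Put another way, 90% power would take 63 practices.

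This rests on a two-sided 5% test, pairwise comparison of arms, 25 patients analysed in every practice and no credit for baseline adjustment. Only the first is inferred from the reproduction of 57; the protocol does not state it. A reader might go further and conclude that the trial is underpowered or must recruit six more practices. The document does not support that, because the right ICC is not established and the planned covariate may make up the difference.

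**What to change.** Use one ICC in section 1.3.6.3, in either of two ways.

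1. Keep 0.04 and give its source, for example that it is a covariate-adjusted ICC, and explain how it relates to the 0.05 called typical.
2. Use 0.05, keep 57 practices and restate the power. Suggested wording: *with an ICC of 0.05, 57 practices (19 per arm) and 25 patients per practice give about 88% power (normal approximation) or 86% (t-based) to detect 0.3 SD at the two-sided 5% level; with an ICC of 0.04 the figures are 91% and about 90%.*

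If baseline adjustment is to be counted, the assumed correlation and its source should be stated.

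The cost is one paragraph of protocol text and, under the second option, a slightly lower power figure. Neither option changes the number of practices, the design or the analysis.

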1.3.6.4 Strategies for improving compliance

The commitment of general practitioners and practice staff will be crucial to the success of the study. Educational events will be used to introduce the study protocol to health professionals from the participating practices. A regular newsletter to practices will report on progress in the study. Financial support will be provided to practices to identify and recruit patients. CPD accreditation will be sought for in-practice training. An educational meeting (again accredited) for participating practices will be held at the end of the study to disseminate findings and recommended strategies.

We believe that the availability of "rescue" medication for patients randomised to the diet and lifestyle arms will reduce the risk of non-consent or loss to follow-up, due to anxieties about not being able to use medication.

1.3.7 Statistical analysis

Analysis will be on an intention-to-treat basis. No sub-group analyses are planned. The data will be analysed using mixed effects models, accepted practice for the analysis of data from cluster randomised trials³¹. Variation between practices and variation between patients nested within practices will be fitted as random effects. The difference between treatment strategies (i.e. the three arms of the trial will be fitted as fixed effects. Most of the outcome variables (e.g. quality of life scores, number of days with (or without) symptoms are continuous and will be analysed assuming a Normal error structure. The dependent variable in each model will be point of follow-up (three, six and twelve months outcomes for quality of life, symptoms and perceptions of bowel function; twelve months for consultation and prescription rates). For each patient, baseline data will be included as a co-variate. The mixed models will be used to generate interval estimates for the differences between alternative treatment strategies.

1.3.8 Economic evaluation

1.3.8.1 Perspective of the evaluation

We will conduct a cost-effectiveness analysis, placing particular emphasis on the subset of costs and effects relevant to address the health service perspective at a macro level. We will supplement this by an individual participant perspective. Our selected outcome measures include condition- and treatment-specific quality of life and a generic utility-based measure of health state, measured at the individual level. We will also record the costs of the condition and its management which are met directly by the patients themselves.

1.3.8.2 Measure of benefits used and type of study

Considering all the measures of effectiveness estimated within the clinical trial, a cost-consequence analysis³³ will be outlined alongside the cost-effectiveness analysis. In the cost-consequence analysis, clinical and QoL profile scores, resources used for the implementation of the intervention strategies and related costs will be presented in a disaggregated way. For each arm of the trial, the breakdown of costs and outcomes will be listed in a tabular format; no summary measures will be presented. This type of evaluation and presentation provides readers with a more transparent interpretation of the results and allows them to make a more selective application of the findings to specific decision-making contexts.

Although quality of life is an important indicator of benefit in the treatment of constipation, and is the primary outcome measure in this study, none of the currently available condition-specific measures yield a unique QoL score. A comparison/synthesis of costs and outcomes based on each of the separate QoL dimensions in our chosen profile measures would be methodologically invalid. For this reason, a utility-based, index measure – the EQ-5D^{26;27} – will also be used, to facilitate calculation of Quality Adjusted Life Years (QALYs). We are, however, aware of the concerns about the use of QALYs in devising resource allocation strategies between different age cohorts. Therefore, we aim to develop or apply already existing ‘corrective’ measures to the results we will obtain, so that our findings will not have unfavourable implications for the funding of health technologies for older people.

Furthermore, we anticipate that the EQ-5D may not be sensitive enough to detect differences in the population being studied. Therefore, alongside this utility-based measure, we will calculate discomfort-free days (DFDs) as a new measure of outcome. This measure will include the impact on patients’ wellbeing of unwanted symptoms due to both constipation and treatment side-effects. It will be a crude but meaningful measure of the patients’ perceived effectiveness of treatment. DFDs will be derived through the self-completed structured diaries, in which patients will be asked to report the overall impact of both the symptoms of constipation and side-effects of the laxatives on their wellbeing. Severity of impact will be graded in levels, and the number of days spent in each level of discomfort will be calculated. This information will be used to assess correlation with DFDs responses. We believe that the comparison of DFDs with EQ-5D utilities will represent a useful addition to the body of knowledge on the assessment of cost-effectiveness in trials where the main impact is expected to be on palliation of symptoms and improvement of the quality of life, rather than on extension of life.

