1.3.3 Health technologies being assessed

1.3.3.1 Treatment strategies at the patient level

Study participants will be randomised to one of three treatment strategies (1.3.1).

Within the laxatives arm, free choice of class of laxatives will be allowed. There is at present insufficient evidence^{10;11} of the relative superiority of one class of laxatives over another, or of combination therapies as opposed to single preparations. Free choice of laxative therapy will more closely replicate the situation which will pertain in routine clinical practice; adherence to treatment protocol is therefore expected to be better than where a change in drug is required. For similar reasons, leeway in dosage will be permitted, within dose ranges commonly used in clinical practice. To minimise the risk of prescribing sub-therapeutic doses, the intervention protocol will remind participating GPs of the therapeutic dose ranges for the available laxative preparations.

The dietary and lifestyle interventions will be informed by findings from previous trials of diet and lifestyle interventions^{1;2;6;7}. They will also draw upon theories of individual behaviour change, including the concept of self-efficacy¹² and the stages of change model⁴.

In both the standardised and personalised arms, the 'information package' will comprise practical, target-based advisory sheets on: diet – increased consumption of non-starch polysaccharides (NSP (fibre)) of both cereal and fruit and vegetable origin¹³ and of bread and bran products¹⁴; hydration¹⁵; dentition¹⁶; mobility and exercise^{17;18}; abdominal massage¹⁸; toilet habits¹⁷; what constitutes normal bowel function¹⁹; the action and potential side-effects of laxative use. Locality-specific information (e.g. details of local exercise programmes for older adults and of fruit-and-vegetable buying clubs) will be included in the package for those allocated to the personalised dietary and lifestyle intervention.

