In both arms, this package will be delivered by practice or community nurses (according to local custom). Appointments will generally be offered at the surgery, though home visits will be an option where appropriate. In the standardised, non-personalised arm, there will be a single short (maximum of 10 minutes) appointment, with delivery of a standard pack of information and brief, general explanation of these information materials. In the personalised arm, there will be an initial long (30-45 minutes)⁵ appointment (though this may be undertaken in two shorter appointment should clinic time so dictate) and the technique of 'motivational interviewing' – 'a directive client-centred counselling style for eliciting behaviour change by helping clients to explore and resolve ambivalence'⁵ – will be employed. The personalised approach will include a patient-specific assessment of barriers to and facilitators of change and delivery of a personalised pack of information with individual targets. Patients in this arm will receive a follow-up motivational telephone call from the nurse at one week and one month after initial appointment.

A potential threat to patient recruitment and retention in this trial is patients' unwillingness to forego medication. For this reason, although diet and lifestyle will be the first-line treatment for patients allocated to those arms, the option of continuing laxative use (either prescribed or over-the-counter) will be available if required; the need for and use of such medication will be captured in patient diaries (1.3.5.1 and 1.3.5.3).

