1.3.5.3 Methods of data collection

1.3.5.3.1 Base-line assessment (W⁰)

Prior to any assessments being conducted, each participant will speak on the telephone with a member of the research team and be invited to discuss any aspect of participation in the study they wish. Once informed consent has been obtained the baseline assessment will be conducted. This assessment will include a short telephone structured interview and a short self completion questionnaire. Current bowel function (based on Rome criteria), fluid and fibre intake and patients' self-perceptions of whether they are currently constipated and levels of anxiety and depression²⁸ will be elicited and data on activities of daily living²⁹, condition-specific quality of life and laxative use (both prescribed and over the counter) will be collected. A weekly structured self-completed diary will be distributed and explained. The person conducting the baseline assessment will notify practices that patients are ready to begin the intervention (as per protocol) and practices will make an appointment to see participants to start the intervention. In following this approach we minimise the risk of patients who have not given informed consent receiving the intervention as the intervention will only be delivered once a signed copy of the consent form is sent to the practice with the instruction to begin the intervention. At this first appointment, treatment per intervention protocol (1.3.5.4) will be initiated. Should patients decide to withdraw when they return to collect either their laxative prescription or for their diet and lifestyle appointment, the practice will notify the research team and all baseline assessment data and patient identification data will be destroyed or deleted from the study database.

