1.3.5.4 Participants' pathways through trial

		Activity
1		Potential participants identified from computerised practice databases using simple electronic query to flag individuals receiving prescriptions for constipation (3 or more in previous 12 months).
2		Initial screen by practice to identify clear exclusions.
3		Written invitation sent by practice (facilitated by research team) to patient to participate in study. Contact details form and pre-paid envelope included for patients wishing to join the study included. Research team to contact patient to answer questions and explain about process for informed consent. Consent form posted to patient with pre-paid envelope. Self completion questionnaire and pre-paid envelope also sent. Control patients will receive their diary (including pre-paid envelope) at this point.
4	W^0	When consent form is returned the telephone baseline interview will be conducted. patient advised to expect contact from practice to arrange 'intervention start' appointment.
5	W^1	Appointment at practice – laxative prescription issued or diet and lifestyle intervention initiated. All patient information and baseline data destroyed by research team if patient notifies practice of their wish to withdraw from study.
6	W^2	One week reinforcement phone call from nurse to patients randomised to personalised diet and lifestyle advice
7	W^{3-4}	Intervention fidelity measure – a small sample of patients in the standardised and personalised intervention arms of the trial will receive a short postal questionnaire to ask about the diet and lifestyle advice.
8	W^5	One month reinforcement phone call from nurse to patients randomised to personalised diet and lifestyle advice
9	W^{12}	Three month follow up outcome assessment (postal questionnaire) and collection of cost data and personal levels of success (telephone interview)
10	W^{26}	Six month follow up outcome assessment (postal questionnaire) and collection of cost data and personal levels of success (telephone interview)
11	W^{52}	Twelve month follow up outcome assessment (postal questionnaire & 1-week symptom diary). Review of practice notes to abstract data on consultation rates and prescription patterns.

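### As described, the diary question behind discomfort-free days asks about side-effects of laxatives but not about unwanted effects of the diet and lifestyle advice that two of the three arms receive

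*Protocol*

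**What the plan says.** Protocol section 1.3.8.2 adds DFDs because the EQ-5D may prove too insensitive in this population. It gives their scope as follows: "This measure will include the impact on patients’ wellbeing of unwanted symptoms due to both constipation and treatment side-effects". On the source it says: "DFDs will be derived through the self-completed structured diaries". In those diaries patients are to "report the overall impact of both the symptoms of constipation and side-effects of the laxatives on their wellbeing". The impact is graded in levels, and the days at each level are counted.

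Section 1.3.3.1 sets out the treatments. Both advice arms receive an information package whose dietary part promotes "increased consumption of non-starch polysaccharides (NSP (fibre)) of both cereal and fruit and vegetable origin", together with bread and bran products, and which also covers hydration, exercise and other habits. Diet and lifestyle is the first-line treatment in those arms, although "the option of continuing laxative use (either prescribed or over-the-counter) will be available if required".

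Table 1 (section 1.3.5.1) separately lists abdominal pain, nausea, bloating, flatulence and diarrhoea as adverse events recorded in the diary, with no attribution to a treatment.

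Section 1.3.8.4 makes health utilities or DFDs the test of whether one strategy is superior. Without such evidence, the analysis becomes one of cost-minimisation.

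On handing out the diary, section 1.3.5.3.1 says of the baseline assessment: "A weekly structured self-completed diary will be distributed and explained". Step 3 of the pathway in section 1.3.5.4, which precedes W0, says: "Control patients will receive their diary (including pre-paid envelope) at this point". Section 1.3.5.3.2 has the diary completed daily for six months starting at W0.

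**The concern.** An outcome that compares treatments should ask every arm about the unwanted effects of whatever treatment that arm was given. Here the stated scope does so, but the described question does not. A patient in the laxative arm who has cramps from the laxative is asked about them. A patient in an advice arm who is bloated after adding bran, and who answers the question literally, has nothing to report unless the bloating is seen as a symptom of constipation. Patients are not blinded (section 1.3.5.5), so they know which treatment they are following and can attribute symptoms to it.

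The gap therefore follows allocation. Where it operates, it makes the advice arms look more comfortable than they are. That could create an apparent advantage for advice, or hide one for laxatives, in a measure on which the adoption recommendation partly rests. Because the protocol doubts the sensitivity of the EQ-5D, DFDs may turn out to be the measure that decides.

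**Working it through.** The protocol states no figure on this point, so there is none to reproduce. The check is a comparison of its own statements, followed by the form that the bias would take.

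**Step 1: scope against question (both in section 1.3.8.2).**

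| Element | Stated scope of DFDs | Question as described |
|---|---|---|
| Symptoms of constipation | covered | covered |
| Side-effects of laxatives | covered | covered |
| Unwanted effects of diet, fibre or lifestyle change | covered, as side-effects of treatment | not covered |

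**Step 2: question against assigned treatment (section 1.3.3.1).**

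| Arm | First-line treatment | Are its unwanted effects asked about? |
|---|---|---|
| Laxatives | laxatives | yes |
| Standardised advice | diet and lifestyle | no; only effects of any laxative also taken |
| Personalised advice | diet and lifestyle | no; only effects of any laxative also taken |

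**Step 3: do other diary fields fill the gap?** The adverse events in Table 1 include bloating and flatulence and carry no attribution, so some of the information is collected. Section 1.3.8.2, however, ties DFDs to the overall-impact question and does not say that the adverse-event fields enter them. The description of diary content in section 1.3.5.3.2 mentions neither adverse effects nor impact on wellbeing.

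**Step 4: form of the bias.** Let D be the number of diary days. Let u be the share of days in an arm on which the only discomfort comes from diet or lifestyle change and goes unreported because it was not asked about. If such days are scored as discomfort-free:

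- recorded DFDs in an arm = true DFDs + D × u
- bias in (advice − laxatives) = D × (u in the advice arm − u in the laxative arm)

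D is about 26 × 7 = 182 days. The protocol gives neither value of u, and it does not state the level of impact at which a day stops being discomfort-free. The sign favours advice if u is larger in the advice arms, which is plausible because only they are assigned the dietary change. The size cannot be derived.

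Between the two advice arms the same gap applies to both, so it cancels to the extent that diet-related effects are equally common in them.

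**Step 5: diary timing.** Section 1.3.5.3.1 issues the diary at the baseline assessment with no distinction by arm. Section 1.3.5.4 posts it earlier, with the consent papers, to a group called control, and does not say when the others receive theirs. No arm is defined as control, and section 1.3.6.3 describes all three as active. Section 1.3.5.3.2 nevertheless starts completion at W0 for everyone. The conflict is about issue, not about the measurement window.

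**The case against.** The strongest reply is that section 1.3.8.2 paraphrases the diary and does not reproduce it. The diary is not in the protocol, and the broader scope stands in the same paragraph, so the printed question may well be right. That lowers confidence that the fault reached patients. It does not remove the conflict between the two descriptions, and the narrower one is the one that says what patients will be asked.

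Three further points would shrink any bias, and all of them stand. Everyone enrolled has a record of repeated laxative prescriptions, and advice-arm patients may go on using laxatives, so the question is not empty for them. Some will report bloating or pain as symptoms of constipation. The unattributed adverse-event fields hold part of the missing information. None of these brings effects of the assigned diet into the question as described.

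It can also be said that DFDs are a new measure that the protocol itself calls crude, and that the primary outcome is untouched. That is true, and it limits the weight of the point, but DFDs remain part of the adoption rule.

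Two stronger readings are tempting and are not supported.

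- A reader might infer that early posting gives one arm a different diary window. One extra week, for example, would be 7/182 = 4% of it. Section 1.3.5.3.2 starts the diary at W0 with no distinction by arm, so receiving it early does not add days, and the 4% has no basis in the protocol.
- A reader might put a number on the wording gap. If 5% to 10% of days were affected, that would be 0.05 × 182 = 9 to 0.10 × 182 = 18 days per patient. Nothing in the protocol anchors those percentages, and the sum also assumes that every such day is missed and that none occurs in the laxative arm.

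**Conclusion.** The point holds for the wording of the question. Section 1.3.8.2 promises a measure that covers side-effects of treatment and then describes a question limited to side-effects of laxatives. As written, the unwanted effects of the assigned treatment are asked about in one arm and not in the other two. This can bias DFDs towards the advice arms.

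The conclusion assumes that the printed question follows the narrower description and that patients answer it literally. The conflict in the text is certain. The direction of any bias is plausible rather than shown, and its size cannot be calculated from the protocol. The consequence is confined to the economic evaluation, where DFDs feed the recommendation in section 1.3.8.4.

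On timing, only an editorial inconsistency remains: two sections disagree on when the diary is issued, and the control label is undefined.

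**What to change.** Use one question, worded identically in all three arms, that asks about the overall impact on wellbeing of symptoms of constipation and of unwanted effects of anything done or taken for it: laxatives, diet or lifestyle changes. Amend the description in section 1.3.8.2 so that it matches the scope already stated there.

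As the editorial correction, reconcile sections 1.3.5.3.1 and 1.3.5.4 on the step at which the diary is issued, preferably the same step in every arm, and name the arm meant in place of the control label. The start of the diary at W0 needs no change.

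The cost is a wording change before printing and a tidier mailing step, with no extra patients, visits or data items. Once diaries worded the narrower way are in use, the missing answers cannot be recovered. The adverse-event fields in Table 1 could then support a sensitivity analysis, but they would not replace the question.
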